2.1.3 Risk/Benefit Assessment

2.1.3.1 Known Potential Risks

2.1.3.1.1 POTENTIAL ADVERSE EVENTS: OPTUNE

Treatment with the Optune is not expected to cause any serious side effects. However, it is possible that treatment may cause any of the following:

- Local warmth and tingling “electric” sensation beneath the transducer array
- Allergic reaction to the adhesive or the gel
- Skin irritation or skin breakdown
- Infection at the sites of electrode contact with the skin
- Transducer array overheating leading to pain and/or local skin burns
- Headache
- Fatigue

2.1.3.1.2 POTENTIAL ADVERSE EVENTS: TEMOZOLOMIDE

Treatment with temozolomide commonly (>30%) causes the following adverse events:

- Headache
- Fatigue
- Nausea
- Vomiting
- Constipation

Treatment with temozolomide commonly (10-30%) causes the following adverse events:

- back, abdominal and/or stomach pain, breast pain
- diarrhea
- alopecia (hair loss)
- dry skin, skin redness, itching and/or rash,
- erythema multiforme (a skin condition that is similar to a bad rash)
- swelling of extremities (arms, legs, fingers, or toes)
- inflammation or swelling of the mouth, throat and/or sinuses
- confusion, amnesia, dizziness, fever, and/or weakness
- anxiety, depression
- joint and muscle pain
- hemiparesis
- asthenia
- coordination abnormal
- viral infection
- insomnia
- changes in sense of taste
- changes in vision such as double or blurred vision
- coughing or shortness of breath, respiratory tract infection
- urinary incontinence/frequency, urinary tract infection
- weight increase

- seizures, hemiparesis (weakness on one side of the body)
- adrenal hypercortisim (elevated hormone levels)
- allergic reactions, sometimes severe
- hepatotoxicity
- lymphopenia, thrombocytopenia, neutropenia, and leukopenia
- anorexia
- convulsions
- Very rare side effects have included secondary cancers (including leukemia and myelodysplastic syndrome (MDS))

2.1.3.1.3 POTENTIAL ADVERSE EVENTS: TEMOZOLOMIDE PLUS OPTUNE

In earlier clinical trials using temozolomide plus Optune, common side effects where Optune and temozolomide were used together were:

- low platelet count
- nausea
- constipation
- vomiting
- fatigue
- medical device site reaction
- headache
- seizures
- depression

In earlier clinical trials where Optune and temozolomide were used together, additional side effects were seen.

- seizure and consecutive seizures
- decrease or loss of ability to carry out daily activities
- neurological decline or death

2.1.3.1.4 ADDITIONAL POTENTIAL RISKS

2.1.3.1.4.1 DISEASE PROGRESSION

Adverse events and complications associated with the underlying disease process, which are unlikely but unknown if related to treatment with Optune together with adjuvant temozolomide include the following adverse events:

- Seizure, including Status Epilepticus
- Neurological and functional decline
- Headaches, nausea and/or vomiting
- Death

2.1.3.1.4.2 CEREBRAL EDEMA

Cerebral edema may be secondary to the disease process itself, the surgical procedure, necrosis from previous radiation, or inflammation due to immune infiltration of the brain or destruction of tumor cells. Symptoms may include, but are not limited to, severe headache, confusion, lethargy, unresponsiveness, coma, or focal neurological deficits. Patients will be monitored throughout the course of the study and those with any signs or symptoms of cerebral edema may need their steroid doses increased, treatment with an osmotic diuretic, or surgical decompression. Edema that fails to respond to aggressive therapy may lead to permanent neurological impairment. The probability of this risk can be predicted to some degree based upon tumor size, location and pre-operative neurological impairment. Patients will be monitored throughout the course of the study.

2.1.3.1.4.3 PHLEBOTOMY

Drawing blood or inserting an intravenous catheter into an arm vein may result in bruising or swelling in the area of the insertion, bleeding at the site of the needle puncture, light headedness, fainting and very rarely, local infection, which may be severe.

2.1.3.1.4.4 MRI

The risks and/or discomforts associated with the performance of MRI include the anxiety produced from being in a tight, enclosed space (claustrophobia). In addition, the machine operates using a large and powerful magnet. The magnetism of the machine attracts certain metals: therefore, people with these metals in their bodies (specifically pacemakers, infusion pumps, metal aneurysm clips, metal prostheses, joints, rods or plates) will be excluded from the study. Patients will also be checked to make sure that they do not bring any metal objects into the MRI facility. Dental fillings are less affected by the magnetic fields generated and are therefore permitted. It will be asked that patients let the physicians conducting this study know of any metal in their bodies other than dental fillings.

2.1.3.1.4.5 ALLERGIC REACTIONS TO CONTRAST AGENTS

During the MRI, patients will be given a contrast agent. The agent is given routinely to obtain enhanced MRI scans of the brain. The agent is administered through the vein and requires the placement of an IV catheter. The catheter placement is similar to drawing blood except that the catheter remains in the vein during the time the agent is actively delivered. The risks of a blood draw and insertion of a catheter are similar. There have been a few, rare cases of allergies to the agent used in MRI contrast-enhanced scans. Patients with any known severe allergies to contrast agents will be scanned using CT instead of MRI. Patients with mild allergies (i.e., rash only) will be pretreated with Tylenol and Benadryl prior to injection of the contrast agent.

2.1.3.1.4.6 CONFIDENTIALITY

Participation in research may result in a loss of confidentiality. All data will be coded to protect the patient's identity; however, records will be made available to individuals involved with the study, the clinical staff administering the study, and regulatory representatives such as the IRB, FDA, OHRP and funding agency. Any publications resulting from this study will not use patient identifying data.

2.1.3.2 Known Potential Benefits

Based on previous studies in GBM with TMZ, increased survival is a potential benefit of Optune in this population of patients with high-risk Grade II and III Astrocytoma.

2.1.3.3 Assessment of Potential Risks and Benefits

Optune is currently FDA-approved as a single modality treatment for recurrent GBM when both surgical and radiotherapy options have been exhausted as well as combination with adjuvant temozolomide for newly diagnosed GBM. In the pivotal EF-11 trial in recurrent GBM, overall survival of patients treated with the device was equivalent to those treated with standard chemotherapy alone [72]. Six-month progression-free survival (6PFS) analysis favored the TTFields arm compared to the chemotherapy arm, although not statistically significant. Safety and toxicity profile favored the Optune arm compared to the chemotherapy control arm. No device-specific grade 3 and 4 toxicities were identified for hematologic, gastrointestinal, vascular, renal and respiratory disorders. There were also no increased grade 3 and 4 central nervous system adverse events. The most common device specific adverse event was skin rash due to the transducer arrays.

Up to 100 patients will be exposed to TTFields treatment during the current trial. Considering the minimal toxicity and promising efficacy seen in the previous trials, the small number of patients exposed to this

treatment in the current study and the poor outcome of these patients despite Temozolomide treatment, we conclude that the possible benefits of TTFIELDS treatment drastically exceed its potential risks.

2.1.3.3.1 EF-14 STUDY EXPERIENCE

Six hundred and ninety five patients from 83 centers across the world were treated. All patients underwent surgery and radiotherapy for the primary tumor. All patients received temozolomide as adjuvant chemotherapy and were then randomized to standard adjuvant TMZ chemotherapy (for 6-12 cycles) with or without concomitant administration of TTFIELDS. During a pre-specified interim and futility analysis after 315 randomized patients reached a minimum follow-up of 18 months there was a 3.1-month PFS increase with a median PFS of 7.1 months compared to 4.0 months in the control group [37].

Increased PFS in the TTFIELDS arm subsequently led to the recommendation from the independent data monitoring committee to terminate the trial early for success and allow standard of care patients to cross over to the TTFIELDS group. The percentage of patients alive at 2 years following enrollment was 43% in the TTFIELDS plus temozolomide group compared to 29% in the temozolomide alone group.

Overall survival results increased from 15.6 months in the temozolomide alone group to 20.5 months in the TTFIELDS plus adjuvant temozolomide group establishing a new standard treatment for newly diagnosed GBM [37].

3 OBJECTIVES AND ENDPOINTS

TABLE 2: OBJECTIVES & ENDPOINTS

OBJECTIVES	ENDPOINTS	JUSTIFICATION FOR ENDPOINTS
Primary		
To determine whether TTFIELDS combined with adjuvant temozolomide increases OS in patients with newly diagnosed Grade II and III astrocytoma with TERT promoter mutation only compared to historical and contemporaneous controls.	OS measured in days from Study Day 0 until death. If the study ends and the participant is still living, OS will be measured in days from Study Day 0.	OS remains the primary concern within this patient population. Intent to Treat analysis will be used to determine if this objective is met.
Secondary		

 To determine whether the combination of TTFIELDS and adjuvant temozolomide is safe in the newly diagnosed high-risk Grade II and III astrocytoma. To determine whether TTFIELDS combined with adjuvant temozolomide increases PFS in patients with newly diagnosed Grade II and III astrocytoma with TERT promoter mutation only compared to historical and contemporaneous controls. To evaluate QOL using KPS, EORTC QLQ-C30/BN20, and MMSE in patients treated with TTFIELDS combined with adjuvant temozolomide compared to 	
 PFS measured in days from Day 0 to progression Safety measured by incidence and severity of Adverse Events and Toxicities. Quality of life measured by KPS, EORTC QLQ-C30/BN20, and MMSE Correlation between % Compliance with TTFIELDS and OS 	Safety, Efficacy, and Quality of Life measures for a more complete view of the effects of the study treatment(s).

historical and contemporaneous controls.		
Tertiary/Exploratory		

 • To determine whether the addition of TTFIELDS to adjuvant temozolomide significantly increase mutation burden, compared to historical and contemporaneous controls. • To determine whether TTFIELDS increases immune cell infiltration. • To determine whether TTFIELDS induces immunogenic cell death in tumor. 	
 • Mutation burden before and after TTFIELDS, compared to historical and contemporaneous controls • Immune cell infiltration before and after TTFIELDS, compared to historical and contemporaneous controls • Immunogenic cell death marker before and after TTFIELDS, compared to historical and contemporaneous controls • Computer modeling of electric field and energy deposition 	To add key immunological and mutational information to the information about these specific tumors.

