
4) Optune therapy should start within two weeks of start of adjuvant temozolomide, but not more than 7 weeks from the end of temozolomide/RT and will be continuous throughout study. Compliance documentation will be obtained every 4 weeks +/- 7 days.
							

5) Every 3 months until death. The only data required during survival follow-up is DOD.
							

6) Biochemistry panel will include electrolytes, creatinine, bilirubin, liver enzymes.
							

7) Patients will begin treatment with temozolomide at 4 weeks (+14 days) from end of radiotherapy. Cycle 1 will be dosed at 150mg/m² daily for 5 consecutive days of a 28-day cycle.
							

Study Procedure:	Screening ≤14 days prior to Day 0	Day 0 : Begin TMZ Treatment	Week 4 (-3/+7 days) and every 4 weeks until treatment stop	Week 8 (±7 days) and every 8 weeks only until treatment stop	Progression	After Treatment Stop (Week 4 (+/- 7 days) from end of treatment)	Survival follow-up

8) Patients will begin treatment with temozolomide Cycle 2 and subsequent cycles every 4 weeks (-3/+7 days) at 200mg/m² PO daily for 5 consecutive days, if CTC hematologic toxicity for cycle 1 is grade < 1 and the CTC non-hematologic toxicity for cycle 1 is grade ≤ 2. If dose escalation is not appropriate, the dose should remain at 150 mg/m² PO daily for 5 consecutive days for Cycle 2 and onward.
							

9) Verification of tissue availability and location should be determined at screening visit. When available, formalin fixed and paraffin embedded (FFPE), pathology slides and/or frozen samples will be obtained for primary tumors and first recurrent tumors.
							

10) Labs to be completed within 3 days for pre-TMZ cycles. Screening and other labs are within the visit windows noted. Pregnancy Test required for WOCBP only at Screening.
							

11) DICOM images will be shipped to Beth Israel Deaconess Medical Center for electric field mapping analysis at baseline, first progression and second progression. Imaging performed between shipping time points should be included in the next shipment.
							

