6.1.2.5 Treatment after temozolomide discontinuation

Following temozolomide discontinuation due to toxicity or radiological disease progression (based on local interpretation of MRI), patients will be offered second line therapy for their disease. The following treatment options may be considered based on the patient's clinical condition per the treating physician's discretion:

1. Re-operation (TTFIELDS treatment will be interrupted for at least 2 weeks after reoperation or until wound healing is sufficient to resume).

2. Local radiation therapy
3. Second line therapy (at the discretion of the treating physician and not limited to traditional cytotoxic chemotherapy)
4. Combination of the above

TTF treatment will continue concomitant with second line treatments until second disease progression for TTFIELDS + temozolomide patients.

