6.1.2.6.1 RECOMMENDATIONS FOR USE OF OPTUNE

All patients treated with Optune will be required to shave their heads to initiate array placement and Optune therapy. Array placement will be performed based on the transducer array map calculated during treatment planning. It is recommended that treatment with the device be continuous with breaks allowed for personal needs (e.g., showering, array exchange). Breaks should be no more than 1 hour twice daily.

Use compliance is aimed at a minimum of 50% (12 hours) with the goal of achieving at least 75% (18 hours) of the time per day on average. In addition, investigators may grant brief breaks in device treatment that last no more than 3 days in any 30-day period at the investigator's discretion. Subjects should be counseled by study staff if compliance reports show less than 50% compliance.

Optune is programmed by Novocure to deliver 200 kHz TFields in two sequential, perpendicular field directions at a maximal intensity of 707 mARMS. There will be no adjustments made to the device by investigators or patients/caregivers.

It is recommended that patients replace the transducer arrays 2-3 times per week with the help of a caregiver. At each array replacement, it is recommended that the patient's scalp be re-shaved and skin treated according to the guidelines in section "Skin Care Guidelines."

There will be no dose adjustments to the device for adverse events. Reasons for breaks in treatment for longer than 24 hours will be documented.

Optune therapy will be stopped in the following cases:

- The occurrence of serious adverse events probably or definitely related to treatment with TFields
- Clinical and functional deterioration considered by the investigator to be prohibitive of continuing treatment.
- After 24 months or after second progression, whichever occurs first.

Treatment with the Optune does not need to be terminated in the following situations:

- Toxicity due to temozolomide treatment
- Radiological progression alone will not lead to termination of TFields treatment, but to replacement of the temozolomide treatment with best standard of care second line therapy:
 - Re-operation
 - Local radiation therapy
 - Second line therapy

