6.4 Study Intervention Compliance

Temozolomide compliance will be measured by subject self-report.

Optune compliance will be measured on each device and a monthly report provided to the subject and Site Investigator by the DSS.

Optune compliance will be addressed according to the following table:

TABLE 9: OPTUNE COMPLIANCE REQUIREMENTS

Subject Compliance in previous 4-week period per device report	DSS	Study Staff
≥ 75%	n/a	Reinforce good compliance report
74% to 50%	
 ○ Re-train patient on device compliance requirements ○ barriers to compliance will be addressed 	n/a
≤ 49%	
 ○ Re-train patient on device compliance requirements ○ barriers to compliance will be addressed 	Counsel subject during study visit re: need for additional use of device and identify any remaining barriers

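### The secondary endpoint correlating Optune compliance with OS has no exposure window or denominator, and a plain correlation can show a false dose-response

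*Combined protocol and SAP*

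**What the plan says.** Table 2 names the endpoint in one line, "Correlation between % Compliance with TTFIELDS and OS", alongside PFS, safety and quality of life. The synopsis (Section 1.1) does not list it among the secondary endpoints. The same table starts the outcome clock at Day 0: "OS measured in days from Study Day 0 until death".

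Compliance is logged from then on. The Schedule of Activities footnotes say "Compliance documentation will be obtained every 4 weeks +/- 7 days", and Section 6.4 says "Optune compliance will be measured on each device and a monthly report provided to the subject and Site Investigator by the DSS".

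Device use is tied to the course of disease. Section 6.1.2.6.1 lists among the reasons for stopping Optune "Clinical and functional deterioration considered by the investigator to be prohibitive of continuing treatment", and also "After 24 months or after second progression, whichever occurs first". Section 6.1.2.5 adds that "TTFIELDS treatment will be interrupted for at least 2 weeks after reoperation".

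Section 10.2.1 sets out log-rank tests for OS and PFS and Pearson correlations of OS and PFS with electric-field parameters. For compliance it gives no averaging window, denominator, landmark, lag, covariates or rule for censored OS.

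**The concern.** The exposure is collected during the outcome time. A patient who deteriorates may use the device less, and those low-use months make up a large share of a short course and a small share of a long one. Average compliance can then be low because the patient is dying early, which reverses the intended direction of inference.

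The trial has no randomised control, and its contemporaneous controls are patients who declined the device. A positive relation between compliance and survival would be tempting corroboration of the OS comparison, and the plan has no safeguard against that relation arising with an inert device.

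**Working it through.** **Inputs from the documents.** 90 treated patients; control median OS 22 months, used for the treated arm when the device does nothing; Weibull shape k = 2.0 (1.8 as the alternative); 36 months of accrual plus 24 of follow-up, so 24-60 months per treated patient (Sections 10.1 and 10.2). Maximum device time is 24 months. The assumed mean use of 75% is the goal in Section 6.1.2.6.1: "with the goal of achieving at least 75% (18 hours) of the time per day on average".

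**Inputs assumed.** The size, length and shape of any fall in use before progression or death, and the between-patient SD of compliance.

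**Anchor.** The plan gives no figure for this endpoint, so the survival inputs were checked against Table 10 (90 + 90 patients, k = 2.0, one-sided 0.05). With HR = (22/(22+M))^k, M = 6 gives (22/28)² = 0.617. With control follow-up taken as uniform over 20-60 months, expected deaths are 75.1 + 67.6 = 142.7. Power = Φ(0.482 × √(142.7/4) − 1.645) = Φ(1.24) = 0.892, against 0.894 in the table. For M = 4 to 8 the results are 0.647/0.793/0.892/0.949/0.978 against 0.649/0.796/0.894/0.950/0.979. At k = 1.8 they match the table exactly.

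**Mechanism, averaging over time on device.** With usual use c and an abrupt fall f over the last w of T months, mean compliance is c(1 − f·w/T). Take c = 75%, f = 0.5, w = 3:
- T = 6: 75 × (1 − 0.25) = 56.3%
- T = 20: 75 × (1 − 0.075) = 69.4%

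A linear fall halves the loss, giving 65.6% and 72.2%. The shorter course has the lower mean although usual use is the same.

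**Mechanism, off-device months counted as zero over 24 months.** Mean compliance is 75 × T/24: 18.8% at T = 6 and 62.5% at T = 20, with no fall in use at all.

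**Simulation 1.** 2,000 trials per row, no device effect, median 22, k = 2.0, linear fall before death, between-patient SD 15 points and month-to-month SD 5 points. Entries are the share of trials with two-sided p < 0.05 in the favourable direction (nominal 2.5%).

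| Fall before death | Mean r | Time-on-device mean, Pearson | Same, Cox | 6-month landmark, Pearson / Cox |
|---|---|---|---|---|
| none | 0.00 | 2.6% | 2.4% | 2.5% / 2.7% |
| 30% over 3 months | 0.12 | 20% | 14% | 2.4% / 3.3% |
| 50% over 3 months | 0.20 | 46% | 32% | 3.1% / 3.0% |
| 30% over 6 months | 0.22 | 54% | 39% | 5.8% / 4.9% |
| 50% over 6 months | 0.35 | 93% | 80% | 8.1% / 6.2% |
| 70% over 6 months | 0.46 | 99.8% | 97% | 12% / 8.4% |
| 50% over 9 months | 0.46 | 99.5% | 97% | 32% / 19% |

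For the 50%/6-month row, SD 10 gives 99.7% and SD 20 gives 77% (Pearson). The Cox column shows that handling censoring alone does not remove the problem. With off-device months as zero over 24 months, r = 0.74 and the rate is 100% with no fall.

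**Simulation 2.** Falls of 25-75% over the last 2-3 months before a progression-driven stop, with the device stopped at the earlier of 24 months and 0.85 × OS, Spearman test. With median 22 and k = 2.0, favourable false positives ran from about 11% to 100%, against about 3% with no fall. Shape and SD matter. With median 24 and k = 1.8, p < 0.05 occurred in:
- abrupt fall, SD 0.12: 46-100%
- abrupt fall, SD 0.20: 26-100%
- gradual fall, SD 0.12: 14-95%
- gradual fall, SD 0.20: 10-79%

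A 3-month landmark, with median 22 and k = 2.0, cut the rate to about 3-22%.

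**Patients kept.** Being on device at 3 months requires OS above 3/0.85 = 3.53 months: 90 × exp(−ln 2 × (3.53/22)²) = 88.4.

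**What a landmark leaves.** If early compliance has a latent correlation of 0.2 with prognosis and there is no fall, the 6-month landmark still gives 34% (Pearson) or 35% (Cox).

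**Censoring.** A plain correlation treats censored OS as complete. Expected deaths among 90 patients followed for 24-60 months are 78.4 at median 22 and 67.6 at median 28, so 1 − 78.4/90 = 13% or 1 − 67.6/90 = 25% are censored.

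**The case against.** A reader might infer that Table 2 prescribes a whole-course average. It does not: it gives no window, and Sections 6.1.2.6 and 6.4 otherwise treat compliance as a measure per 4-week period. The missing definition is part of the defect, and the two natural ways of filling it are both exposed to bias.

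A reader might also infer that use is known to fall as patients decline. The documents do not say so. The rules on deterioration and reoperation concern stopping and interrupting the device. Stopping does not in itself lower a mean taken over time on device and may cut off low-use months, while retraining below 75% and counselling below 50% (Table 9) work against a decline. The fall is a plausible inference and its size is unknown.

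Nor do the figures support saying that a false dose-response will appear. With a time-on-device mean and no fall the rate is nominal; with a gradual 25% fall and a wide SD it is about 10%. The bias also does not persist under every method, since landmark and lagged analyses are available.

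Finally, the endpoint is absent from the synopsis and carries no alpha or stated causal claim. That limits the consequence. It does not supply the missing safeguard.

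**Conclusion.** The point holds in conditional form. Compliance accrues after the OS origin, device use depends on disease course, and nothing in the plan guards against reverse causation. For falls of 25-75% over the last 2-3 months, the favourable false-positive rate is roughly 10-100% against a nominal 2.5%, depending on whether the fall is gradual or abrupt and on a between-patient SD of 0.12-0.20. With no fall and averaging over time on device, it is nominal. If off-device months count as zero over 24 months, it was 100% without any fall, because survival time is then built into compliance.

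These figures rest on assumed patterns of decline. The direction of the bias and the gain from a landmark held across the simulated falls. The primary intent-to-treat OS comparison is not affected.

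**What to change.** Redefine the endpoint in Table 2 and add its analysis to Section 10.2.1:
- **Exposure:** mean % device use from device start to week 12, with the time from device start to week 12 as denominator. This matters because Optune may start up to two weeks after temozolomide.
- **Outcome and population:** OS counted from week 12, in patients alive and on device at week 12.
- **Model:** Cox regression, which handles censored OS, adjusted for baseline KPS, steroid dose, MGMT status and extent of resection.
- **Sensitivity analysis:** time-dependent compliance lagged by at least 8 weeks. A decline longer than the lag would be only partly removed.
- **Label:** exploratory and non-causal. A landmark removes most reverse causation but not prognostic confounding, and covariates reduce that only in part.
- **Consistency:** bring the synopsis and Table 2 into agreement on whether this is a secondary endpoint.

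The cost is a protocol and SAP wording amendment with IRB approval. No visits are added: compliance reports, KPS, steroid dose, MGMT status (where feasible) and operative reports are already collected. About 2 of 90 patients drop out of this one analysis. That count covers death and progression-driven stops only; early stops for other reasons would add to it, and the documents give no rate for them.
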